16.1.2. MISSING DATA IMPUTATION METHOD FOR PRIMARY EFFICACY ENDPOINT

No missing data imputation method will be used for primary efficacy analysis. For participants who withdraw from the study prior to having met the criteria for the primary efficacy endpoint. Participants will be censored (considered as not having the event) at the time of last observation.

Sensitivity analyses will be explored to assess the robustness of treatment effects for the primary efficacy endpoint, where different missing data mechanisms will be explored using multiple imputation approaches. Full details of the sensitivity analyses are specified in Section 16.1.5.

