16.1.4. PRIMARY ANALYSIS OF PRIMARY EFFICACY ENDPOINT

The primary efficacy analysis of the primary endpoint will be performed on the FPAS. Participants who withdraw from the study prior to having met the criteria for the primary efficacy endpoint will be censored (considered as not having the event) at the time of last observation. Participants with deaths that are caused by SARS-CoV-2 (death related to COVID marked on the death eCRF page) will be considered as having the event, even if no other qualifying symptoms are met. Participants with hospitalizations due to COVID-19 will also be considered as having the event.

A Poisson regression model with robust variance (Zou, 2004) adjusting for follow-up time, will be used as the primary efficacy analysis model to estimate the RR on the incidence of SARS-CoV-2 RT-PCR-positive symptomatic illness occurring post dose of IMP between the AZD7442 and the placebo groups. The model contains the planned treatment group and age group at the time of informed consent (i.e., ≥ 60 years and < 60 years, see Section 7.6) as a covariate. The logarithm of the participant's corresponding follow-up time at risk starting from dose up to the study day 183 visit will be used as an offset variable in the model to adjust for participants having different exposure times during which the events occur. Participants who withdraw or have a non-COVID-19 related death prior to meeting the primary endpoint will not be counted as having the event. The follow up time for those participants will be at that time relative to dose. Calculation of follow-up time is detailed as following:

- For participants who meet the primary endpoint before Day 183, the follow-up time will be calculated as (Date of Onset of Primary Endpoint) (Date of Dosing) + 1. Date of Onset of Primary Endpoint is defined as the assessment date of qualifying COVID symptoms, if associated with a positive SARS-CoV-2 RT-PCR lab test from a sample collected within the 5 days prior to symptom assessment through 10 days after symptom assessment. In the case of death due to COVID-19 or hospitalization due to COVID-19, the Date of Onset of Primary Endpoint is the earliest date of death/date of hospital admission when a qualifying symptom assessment is not observed.
- For participants who do not experience a primary endpoint before Day 183, the efficacy follow-up time will be considered censored and determined based on the following:

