 - o If an end of study date occurs prior to Day 183, the efficacy follow-up time will be calculated as (Date of End of Study or Date of Last Assessment, whichever is later) (Date of Dosing) + 1.
 - o If an end of study date occurs after Day 183, the efficacy follow-up will be censored at Day 183.

For participants who continue to participate in the study at the time of the primary analysis, the DCO date will be used as their last assessment date. For participants with no post-baseline visit data available, the date of IMP administration will be used i.e. follow-up will be 1 day.

Efficacy is the incidence of infection in the AZD7442 group relative to the incidence of infection in the placebo group, expressed as a percentage. Efficacy will be calculated as relative risk reduction (RRR) = 100% x (1 - relative risk).

RRR and its corresponding 2-sided 95% CI will be estimated from the Poisson regression model with robust variance. In addition, the 2-sided p-value testing null hypothesis that there is no difference in efficacy between AZD7442 and placebo (i.e. the efficacy is equal to 0) will be obtained from the model. Statistical significance will be achieved if the lower bound of the 95% CI for efficacy is > 0, which corresponds to an observed two-sided p-value < 0.05. For the final analysis nominal 95% CI's will be presented.

The Poisson regression with robust variance analysis will be implemented by using the SAS PROC GENMOD procedure with the REPEATED statement for participant ID and logarithm link as well as OFFSET option. The estimated parameter $\hat{\beta}$ [i.e., log(RR)], 2-sided 95% confidence interval (CI) for $\hat{\beta}$, and the 2-sided p-value will be obtained from the SAS outputs. The estimated RR and corresponding CI for the RR is given by exponentiating $\hat{\beta}$ and its confidence limits. Therefore, the percent of RRR is given by $[(1 - \exp(\hat{\beta})) * 100\%]$. The CI for the percent of RRR is given by ([1 - exp(upper confidence limit for $\hat{\beta}$) * 100%], [1 - exp(lower confidence limit for $\hat{\beta}$) * 100%]).

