- If the participant does not experience a primary endpoint event and also has no intercurrent event, then no imputation is performed, and data is considered up to Date of End of Study or Date of Last Assessment, whichever is later. If an end of study date or date of last assessment occurs after Day 183, the efficacy follow-up will be censored at Day 183. For participants who continue to participate in the study at the time of the primary analysis, the DCO date will be used as their last assessment date. For participants with no post-baseline visit data available, the date of IMP administration will be used i.e. follow-up will be 1 day.
- If the participant has an intercurrent event before Day 183 and before a primary endpoint event:
 - O Step 1: The missing event status will then be imputed using a single imputation from the Bernoulli distribution, where the probability that the participant experiences the primary endpoint is the event rate observed in the subset of participants who did not have an intercurrent event in the same arm and age group. For participants in the placebo group: $p_{Placebo} = \frac{E_{Placebo,no \, IE}}{N_{Placebo \, no \, IE}}$, where: $E_{Placebo,no \, IE}$ is the

number of participants in the placebo arm who experience a primary endpoint event and did not experience an intercurrent event; $N_{Placebo,no\ IE}$ is the number of participants in the placebo arm who did not experience an intercurrent event. The value of $p_{Placebo}$ will be calculated separately for each age group within the placebo arm. For participants in the AZD7442 group: $p_{AZD7442} = \frac{E_{AZD7442,no\ IE}}{N_{AZD7442,no\ IE}}$, where: $E_{AZD7442,no\ IE}$ is the number of participants in the AZD7442 arm who experience a primary endpoint event and did not experience an intercurrent event; $N_{AZD7442,no\ IE}$ is the number of participants in the AZD7442 arm who did not experience an intercurrent event. The value of $p_{AZD7442}$ will be calculated separately for each age group within the AZD7442 arm. If there are zero events observed in a given age group in a given arm, then the event rate used for imputation will be the armspecific event rate (pooled across both age groups). The random seed is 23456.

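### The primary-model follow-up formula runs to the later of end of study and last assessment, while other SAP text censors at last observation, so for some lost participants time with little or no case ascertainment can enter the offset.

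*SAP*

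**What the plan says.** The SAP gives more than one rule for participants who leave without a primary endpoint event.

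- **Last observation.** Section 16.1.2: "Participants will be censored (considered as not having the event) at the time of last observation". The first paragraph of 16.1.4 repeats it: such participants "will be censored (considered as not having the event) at the time of last observation".
- **Time of withdrawal or death.** Later in 16.1.4, for those who withdraw or die of a cause other than COVID-19: "The follow up time for those participants will be at that time relative to dose".
- **Later of two dates.** The first follow-up bullet of 16.1.4, for an end of study before Day 183: "the efficacy follow-up time will be calculated as (Date of End of Study or Date of Last Assessment, whichever is later". Section 16.1.8.1 has the same wording for participants with neither an endpoint event nor an intercurrent event: "data is considered up to Date of End of Study or Date of Last Assessment, whichever is later".
- **Day 183.** The second bullet of 16.1.4: "If an end of study date occurs after Day 183, the efficacy follow-up will be censored at Day 183". It makes no reference to the last assessment.
- **One day.** Also in 16.1.4: "For participants with no post-baseline visit data available, the date of IMP administration will be used i.e. follow-up will be 1 day".

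The result matters because the logarithm of "follow-up time at risk starting from dose up to the study day 183 visit will be used as an offset variable" in the primary model. Section 16.1.3 separately censors at unblinding or first COVID-19 preventive product, whichever is earlier. No section reconciles these rules, and neither last observation nor end-of-study date is defined.

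**The concern.** The offset is meant to be time at risk, that is, time during which a case could have been counted. After contact with a participant stops, a symptomatic PCR-confirmed case is unlikely to reach the database. If the end-of-study date is entered some weeks after the last contact, the later-of-two-dates formula credits those weeks as event-free follow-up. This lowers the estimated rate in that arm.

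The SAP also treats similar participants differently. Someone never seen after dosing contributes 1 day. Someone seen once on Day 8 and closed out on Day 120 contributes 120 days.

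If loss or lag differs between arms, the relative risk shifts. Even without a shift, two programmers following different sentences of the same SAP would build different offsets for the primary analysis. The definition also reaches beyond the primary endpoint: 16.2.5 analyzes the other secondary efficacy endpoints in the same manner, including through Day 366.

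**Working it through.** **1. The plan's own figures.** Table L (SAP 7.1) gives simulated power for 80% efficacy with 3433 AZD7442 and 1717 placebo participants. It was re-simulated with 200,000 trials per row, the total number of events fixed and a two-sided 5% level. The variance of log RR was 1/x₁ − 1/n₁ + 1/x₀ − 1/n₀.

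| Events | Table L | Re-simulated, tabulated rates | Re-simulated, RR exactly 0.20 |
|---|---|---|---|
| 18 | 89% | 88.0% | 88.6% |
| 20 | 96% | 96.8% | 96.4% |
| 22 | 97% | 97.2% | 97.2% |
| 24 | 98% | 97.6% | 97.8% |

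The table reproduces to within 1 point. Its footnote assumes no loss to follow-up, so it neither tests nor depends on the disputed rule.

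**2. One participant (illustrative dates).**
- Last observation Day 60, end of study Day 150: 60 days under the last-observation text, 150 under the first bullet.
- Last observation Day 60, end of study Day 200: 60 days against 183 under the second bullet, a difference of 123 days.

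**3. Arm level.** The documents give no loss rate and no lag, so the following are assumptions: true RR 0.20 (the SAP's 80% efficacy), a fraction w of an arm lost, last observation uniform over Days 1 to 183, end-of-study date g days later, and the offset capped at 183.

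Mean follow-up per participant: T(w, g) = (1 − w) × 183 + w × mean[min(u + g, 183)], with u uniform on 1 to 183.

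Efficacy under the formula: 1 − 0.20 × [T(w_P, g)/T(w_P, 0)] / [T(w_A, g)/T(w_A, 0)], where A is AZD7442 and P is placebo.

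Worked case: w_A = 5%, w_P = 20%, g = 91. The mean of min(u, 183) is 92. The mean of min(u + 91, 183) is (137.5 + 183)/2 = 160.25.
- AZD7442: 0.95 × 183 + 0.05 × 160.25 = 181.86, against 0.95 × 183 + 0.05 × 92 = 178.45. Ratio 1.0191.
- Placebo: 0.80 × 183 + 0.20 × 160.25 = 178.45, against 0.80 × 183 + 0.20 × 92 = 164.80. Ratio 1.0828.
- RR = 0.20 × 1.0828/1.0191 = 0.2125, so efficacy reads 78.75% instead of 80%.

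| Loss, AZD7442 / placebo | Excess person-time, 14-day lag | Efficacy | Excess person-time, 91-day lag | Efficacy |
|---|---|---|---|---|
| 5% / 5% | 0.38% / 0.38% | 80.00% | 1.91% / 1.91% | 80.00% |
| 10% / 10% | 0.77% / 0.77% | 80.00% | 3.92% / 3.92% | 80.00% |
| 5% / 10% | 0.38% / 0.77% | 79.92% | 1.91% / 3.92% | 79.61% |
| 5% / 20% | 0.38% / 1.63% | 79.75% | 1.91% / 8.28% | 78.75% |
| 10% / 30% | 0.77% / 2.59% | 79.64% | 3.92% / 13.15% | 78.22% |
| 10% / 5% | 0.77% / 0.38% | 80.08% | 3.92% / 1.91% | 80.39% |

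**4. A second set of assumptions.** Here follow-up to data cut-off was 60 to 180 days, the lag 30 to 90 days, and loss 15% on placebo against 5% on AZD7442. The RR is multiplied by 1.023 to 1.051. Starting from the 77% in Protocol 2.3.2 (RR 0.23), 0.23 × 1.023 = 0.235 and 0.23 × 1.051 = 0.242, so efficacy would read 76.5% to 75.8%.

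**The case against.** The best defense is that the bullets are the operational definition. Section 16.1.4 introduces them as the detailed calculation, last observation is not defined elsewhere, and two other places support a study-exit date: the sentence on withdrawals and non-COVID-19 deaths in 16.1.4, and SAP 5.2, which includes participants who withdraw consent up to their study termination. This stands to the extent that the SAP holds competing rules, not one clear rule and a slip. It does not remove the conflict, because a study-exit date and a last observation can differ.

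Four further points limit the reach:

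- An active withdrawal is usually itself a contact, so it adds little unobserved time. The problem is mainly participants declared lost.
- A participant known to have been unblinded or vaccinated is already censored at that date under 16.1.3. A placebo participant who leaves to be vaccinated is exposed to the rule only if no such date is recorded.
- The lag depends on how sites date the end of study. The SAP rests on the parent protocol, which is not among the documents. Section 7.3 of the sub-study protocol describes repeated contact attempts before a participant is considered withdrawn, but sets no dating convention. If sites enter the date of last contact, the rules agree.
- Ascertainment after last contact need not be nil. Deaths and hospitalizations due to COVID-19 count as events under 16.1.4 and may come to light later.

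The multiple-imputation analysis in 16.1.5 covers withdrawals, but it imputes event status and does not restate the follow-up time. The absolute risk reduction in 16.1.6 uses a score method on proportions, so the offset does not affect it.

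**Conclusion.** The inconsistency is real and sits in the primary model's offset. Where the end-of-study date follows the last contact, the formula credits time with little or no case ascertainment, against the SAP's own description of the offset as time at risk. The second bullet has the same weakness when contact stopped before Day 183.

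The consequence is small. Efficacy does not move if loss and lag are equal between arms. It moves by up to about 1.8 points in the most unequal case tried (10% loss on AZD7442, 30% on placebo, 91-day lag). Every loss rate and lag here is assumed.

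A reader might infer that the reported efficacy of 77% (95% CI 46 to 90, Protocol 2.3.2) is biased, or that all withdrawals inflate the denominator. The documents support neither. They give no loss by arm and no dating convention, and the shifts calculated are small beside that interval. A reader might also assume that the Cox and Kaplan-Meier analyses share the same censoring times. Section 16.1.6 does not say so.

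**What to change.** Define the censoring date once, for participants no longer in the study who had no event: the last visit or documented contact at which COVID-19 status was ascertained, or the date of death for non-COVID-19 deaths. Cap it at Day 183, the data cut-off and any intercurrent event. Where 16.2.5 extends the analysis to Day 366, the cap moves with it.

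Apply the definition to both follow-up bullets in 16.1.4, and align 16.1.2 and 16.1.8.1. Changing only the first bullet would still leave 183 days credited to someone last seen on Day 60 whose study end was entered on Day 200.

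If the primary analysis has already been run with the later-of-two-dates rule, say so and rerun it once with the new date as a sensitivity check.

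The cost is slightly less person-time and minor reprogramming. The present formula already needs the last-assessment date. Whether dates of contacts between visits are in the analysis data should be confirmed, since the parent study's schedule is not among the documents.

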2.3.1 Risk Assessment

Based on all available clinical study data with a cut-off date of 20 August 2021, there were no identified risks associated with AZD7442. The current risk assessment for AZD7442 is summarized in Table 6.

Table 6 Risk Assessment for AZD7442

Important Identified Risks	None
Identified Risks	None
Important Potential Risks	None
Potential Risks	Potential risks include injection-related reactions, ADE disease, serious hypersensitivity including anaphylaxis, and cardiac and thromboembolic events.
Reference Safety Information	For AZD7442, no SARs have been identified. Any SAE that is deemed to be related to the IP by the Investigator or the Sponsor will be treated as a suspected unexpected serious adverse reaction and appropriately expedited.

Based on a data cut-off of 20 August 2021.

ADE, antibody-dependent enhancement of disease; IP, investigational product; SAE, serious adverse event; SAR, serious adverse reaction.

In the PROVENT parent study, AZD7442 was generally well tolerated and preliminary analyses showed that overall AEs were balanced between the placebo and AZD7442 groups. A small number of cardiovascular serious adverse events (myocardial infarction and cardiac failure) have been reported in the PROVENT parent study at a higher rate in participants who received AZD7442 compared to placebo. All participants who experienced cardiac SAEs were at high risk for cardiac events, many of whom had a prior history of cardiovascular disease at baseline. There was no clear temporal pattern and a causal relationship between AZD7442 and these events has not been established. There was no signal for cardiac toxicity or thrombotic events identified in the nonclinical studies. Monitoring of cardiovascular events will occur in this sub-study. There were no cases of severe COVID-19 or COVID-19-related deaths in those treated with AZD7442. In the placebo arm, there were 3 cases of severe COVID-19, which included 2 deaths.

In a separate Phase III AZD7442 study STORM CHASER (N = 1121), which enrolled a younger population with fewer baseline cardiac risk factors than PROVENT and no related cardiac SAEs at the time of primary analysis.

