7.1. SAMPLE SIZE CALCULATION

Approximately 5150 participants will be randomized in a 2:1 ratio to receive a single IM dose of AZD7442 (divided in 2 sequential injections, one for each mAb component) (the active group, n = approximately 3433) or saline placebo (the control group, n = approximately 1717) on Day 1.

The sample size calculations are based on the primary efficacy endpoint and were derived following a modified Poisson regression approach (Zou 2004). All participants will be followed for the entire duration of the study.

With at least 18 observed events, assuming 80% true efficacy, the study will have approximately 90% power to demonstrate that the lower bound of the 2-sided 95% CI for efficacy is greater than 0 (see Table L:).

Table L: Simulated Power by Number of Observed Events

$\lambda_{Placebo}$	$\lambda_{AZD7442}$	Observed Events	Simulated Power
0.0074	0.0015	18	89%
0.0082	0.0016	20	96%
0.0090	0.0018	22	97%
0.0098	0.0020	24	98%

Simulated power is based upon 10000 simulations of trials assuming 80% efficacy $\left(1 - \frac{\lambda_{AZD7442}}{\lambda_{Placebo}}\right)$, using Poisson regression model with robust variance, with no participants lost follow-up. Power is the proportion of trials with p-value < 0.05.

The sample size necessary to achieve the power for the primary endpoint is calculated based on the assumed attack rate in the placebo group and the 80% efficacy assumption, using Poisson regression model with robust variance.

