7.3. STATISTICAL TESTS

Statistical tests will be conducted at the two-sided 5% significance level. Confidence Intervals (CIs) will be two-sided with 95% coverage.

The null hypothesis for the primary endpoint is: efficacy of AZD7442 compared to placebo in preventing COVID-19 is equal to 0. Whereas, the alternative hypothesis is: efficacy of AZD7442 compared to placebo in preventing COVID-19 is not equal to 0. That is:

H0: efficacy = 0

HA: efficacy $\neq 0$

Primary efficacy will be presented with a 2-sided 95% CI, and statistical significance will be achieved if the lower bound of the 2-sided 95% CI is > 0. The success criterion for the study will be statistical significance.

If the statistical significance of the primary efficacy endpoint is demonstrated at two-sided alpha of 0.05, formal assessments of the key supportive estimands and key secondary estimand will be conducted at the primary analysis.

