If convergence cannot be achieved with the Poisson regression analysis model with robust variance, the Cochran-Mantel-Haenszel (CMH) will be used as the primary analysis model to test the treatment effect on SARS-CoV-2 RT-PCR-positive symptomatic illness between AZD7442 and placebo groups. The CMH test will be stratified by age group at the time of informed consent (i.e., ≥ 60 years and < 60 years, see Section 7.6). The RR of AZD7442 over placebo for the incidence of SARS-CoV-2 RT-PCR-positive symptomatic illness occurring post dose and the 95% CI will be obtained. The percent of RRR and the 95% CI will be reported following the relationship of RRR

(%) = (1- RR) * 100%. A Breslow-Day test will be conducted, and p-value presented, to evaluate homogeneity of the RRR across strata.

A listing will be provided for all COVID-19 symptom assessments and NP swabs assessed by RT-PCR (both local laboratory and central laboratory samples) regardless of RT-PCR result.

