16.2.5. ANALYSIS OF SECONDARY EFFICACY ENDPOINTS

The key secondary efficacy endpoint will be analyzed as described in Section 16.2.1.

All other secondary efficacy endpoints described in Section 16.2.3 above will be analyzed in the same manner as the primary analysis of the primary efficacy endpoint (refer to Section 16.1.4), prior to Day 183. These analyses will be repeated for these endpoints through Day 183 and through Day 366.

The key secondary efficacy endpoint will be assessed by a hierarchical order. More details on multiplicity control are described in Section 7.4. For the other secondary efficacy endpoints, the 95% CIs and p-values will be nominal as they are not controlled for multiplicity.

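### For the rare secondary endpoints and sparse subgroups, the SAP has no rule for an arm with zero events; the robust Poisson model can then report convergence with a near-zero p-value and a degenerate confidence interval

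*SAP*

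**What the plan says.** SAP 16.1.4 estimates the relative risk from a log-link Poisson model with robust variance, terms for treatment and age group, and log follow-up time as an offset. The estimate, interval and p-value come from PROC GENMOD with a REPEATED statement. Only if convergence fails does the plan change: "the Cochran-Mantel-Haenszel (CMH) will be used as the primary analysis model". The CMH analysis is stratified by age group, has no follow-up term, and must yield a relative risk with a 95% CI.

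SAP 16.2.5 says that the other secondary efficacy endpoints, severe or critical COVID-19 and COVID-19-related emergency department visits, "will be analyzed in the same manner as the primary analysis of the primary efficacy endpoint". Their p-values and intervals are nominal. SAP 16.2.7 adds Kaplan-Meier curves with a log-rank p-value.

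SAP 16.1.7 uses the robust Poisson model within subgroups, and 16.2.8 extends this to subgroups of the secondary endpoints. The provisions there and in 7.7 for sparse data act when a model does not converge, or, for CMH in 16.1.7, when the primary analysis itself used CMH. The one rule for zero events is in 16.1.8.1, and it concerns imputation for the hypothetical estimand.

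The protocol, a sub-study addendum, gives parent-study results in 2.3.1: "There were no cases of severe COVID-19 or COVID-19-related deaths in those treated with AZD7442". It reports 3 severe cases on placebo.

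**The concern.** Non-convergence is the wrong alarm for an empty arm. The maximum-likelihood log relative risk is then minus infinity, and iteration stops at an arbitrary large negative number. Fitted values and residuals in the empty arm are almost zero, so that arm adds almost nothing to the sandwich variance. The output is a huge coefficient with a moderate standard error, which reads as overwhelming evidence.

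Severe COVID-19 is a listed secondary endpoint with few expected events, and the counts in the protocol have exactly this pattern. At stake is a published efficacy estimate for severe disease with an interval that shows no uncertainty, based on three events.

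**Working it through.** **Inputs.** SAP 7.3: "Statistical tests will be conducted at the two-sided 5% significance level". SAP 7.1: "Approximately 5150 participants will be randomized in a 2:1 ratio", with "the active group, n = approximately 3433" and "the control group, n = approximately 1717". Protocol 2.3.1: 0 and 3 severe cases. Assumed, because the documents do not give them: all three cases fall in the analysis set and inside the analysis period, analysis-set sizes equal the planned arms, follow-up runs from 30 to 182 days, and 44% of participants are in one age stratum.

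**1. The plan's own power figure.** SAP 7.1 states: "assuming 80% true efficacy, the study will have approximately 90% power" with at least 18 events. Under 80% efficacy and 2:1 allocation, the AZD7442 share of events is (2 × 0.2)/(2 × 0.2 + 1) = 0.2857. Given the total number of events, I enumerated the binomial splits and applied the robust Wald test with variance 1/a − 1/3433 + 1/b − 1/1717, where a and b are the event counts on AZD7442 and placebo.

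| Events | SAP Table L | Recomputed |
|---|---|---|
| 18 | 89% | 88.6% |
| 20 | 96% | 96.4% |
| 22 | 97% | 97.2% |
| 24 | 98% | 97.8% |

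The planning model reproduces. It works when both arms have events.

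**2. Robust Poisson with 0 versus 3.** In an empty arm of n participants with tiny fitted mean m, the sandwich variance is n·m²/(n·m)² = 1/n. The total variance is about 1/3 − 1/1717 + 1/3433 = 0.333, so SE ≈ 0.577, close to 1/√3. The fitted model (statsmodels GEE, Poisson, log link, independence, age term and offset) gave:
- log RR about −22.7, where the value reflects only where iteration stopped
- robust SE 0.58, p numerically 0, convergence flag true
- 95% CI for log RR about −23.8 to −21.5, so the relative risk reduction is 100% to 100% at any printable precision

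A model-based SE for the same data is about 12,500 (p = 0.999), which shows that the data do not determine the coefficient. Even 0 versus 1 gives p of about 1e−98 or smaller.

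**3. Error rate under no effect, three events in total.** P(no AZD7442 event) = (1/3)³ = 3.7%. P(no placebo event) = (2/3)³ = 29.6%. The model rejects in both cases, so it rejects in 33% of trials instead of 5%. The figure is 56% with two events and 21% with four.

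**4. Exact conditional result, equal mean follow-up.** One-sided p = (1717/5150)³ = 0.037. The two-sided p ordered by probability is also 0.037, and doubling gives 0.074. The central 95% upper limit for the AZD7442 share is 1 − 0.025^(1/3) = 0.708. As a relative risk this is (0.708/0.292) × (1717/3433) = 1.21, so the CI is 0 to 1.21.

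**5. CMH on the same counts.** Expected AZD7442 events are 3 × 3433/5150 = 2.00, with variance 0.666. The chi-square is 2.00²/0.666 = 6.00, p = 0.014. Splitting by age (30% to 70% in one stratum, assumed) leaves this unchanged. Its null rejection rate with three events is 3.7%. The relative risk is 0, so no log-based CI exists.

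**6. Follow-up time.** With 8 versus 17 events, used as an illustration, CMH efficacy is 76.5% whatever the exposure. Rate-based efficacy is 73.8%, 76.5%, 78.6% or 80.4% if the AZD7442:placebo ratio of mean follow-up is 0.9, 1.0, 1.1 or 1.2 (assumed range).

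**7. Primary endpoint.** Under the planning assumptions, the chance of no AZD7442 event is 0.03% to 0.10% at 24 events and 0.2% to 0.6% at 18. Protocol 2.3.2 reports 25 cases and 77% efficacy (46, 90). A split of 8 versus 17 would give 76.5% (45.6, 89.8). That split is inferred, but the finite interval and efficacy below 100% show that neither arm was empty.

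**The case against.** The strongest reply is that little depends on this. The severe endpoint is outside the testing hierarchy, its p-value is nominal, and the log-rank test in 16.2.7 stays usable and respects follow-up time. That stands, and it limits the consequence. It does not repair the relative risk reduction and CI that the plan also requires.

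A reader might infer that the CMH fallback is invalid too. The documents and the arithmetic do not support that. CMH is a defined test with an empty arm. For one to eight events in total, its null rejection rate exceeds 5% only at two events (11.1%) and eight (5.9%). Its faults are narrower: an approximate p-value, no log-based CI at a relative risk of zero, and no person-time.

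A reader might also infer that the primary analysis or every secondary analysis is compromised. Neither follows. The primary endpoint had events in both arms. SAP 16.2.5 refers the key secondary endpoint to 16.2.1 and applies the shared method only to the other secondary endpoints.

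Two reservations remain. SAS was not available, so GENMOD's own convergence message is untested, and the fallback might start there. And the SAP (29 July 2021) predates the protocol's 20 August 2021 data cut-off, so this is a foreseeable gap in the rules, not a choice made with the result in view.

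**Conclusion.** The point holds for severe or critical COVID-19, COVID-19-related emergency department visits and sparse subgroups, whenever one arm is empty. On the protocol's 0 versus 3 counts, the planned model can print certainty (SE 0.58, p numerically zero), where the exact interval for the relative risk runs from 0 to 1.21 and so includes no effect. If the fallback does start, the required 95% CI still cannot be produced by the usual log-based method, so neither branch gives a usable interval.

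The size of the example rests on planned arm sizes, on all three cases counting in the analysis set and period, and on equal mean follow-up for the exact figures. The collapse of the robust SE follows from the algebra and does not depend on the assumed follow-up or age mix. No confirmatory claim is affected.

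**What to change.** In SAP 16.2.5, 16.1.7 and 16.2.8, add a rule triggered by the event count: when either arm, or either arm within a subgroup, has zero events, the CI for relative risk reduction and the p-value come from an exact conditional Poisson analysis with person-time, stratified by age group where data permit. Apply it regardless of the convergence flag.

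State one convention, for example the doubled one-sided p-value with the central 95% CI. For 0 versus 3 that pairs 0.074 with 0 to 1.21. Pairing 0.037 with the same interval would break the correspondence between p-value and CI that 16.1.4 relies on.

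Keep the robust Poisson model for the primary endpoint and wherever both arms have events. A wider trigger, such as fewer than five events in an arm, would be a mistake if it reached the primary endpoint. Under the planning assumptions, AZD7442 would have fewer than five events in 14% of trials at 24 events and 38% at 18, and the model behind Table L would be displaced for a failure shown only at zero.

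The cost is a few sentences and one procedure call. The exact interval is slightly conservative.
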